### *Minimizing the Risk for Subjects*

This project is a comparison of standardized epidural technique between two different epidural catheter kits that are currently in use in major academic institutions in the country and at the University of Michigan. There is no hypothesized difference in the ability to thread the

epidural catheter between the two kits. The research involves no risk to the patient subject beyond risk inherent to epidural placement.

Waiver of informed consent will not affect the rights, welfare, or pain management of the subject, given that in either scenario, they will receive a standard of care epidural.

No identifiable information will be collected and retained about the subjects after completion of the patient's vaginal or cesarean delivery. All data will be recorded using a numerical code to be assigned to each individual study case. The master file will be kept in a locked filing cabinet in the principal investigator's office. All data will be analyzed in a coded fashion. Attention to strict confidentiality will be maintained; no attempts will be made to identify individual study subjects.

### *Potential Risks of Participation*

The risk of participation is the same as the risks of receiving an epidural catheter for analgesia if not enrolled in the study. This study design includes clinical procedures already being performed, with the risks the same as standard epidural placement regardless of which device is used or physician participation in the study. The overall goal for both study groups remains the same: adequate and timely management of labor pain.

For placement of epidural catheter for analgesia, risks include:

- Inadequate pain control; likely, but it is not serious as it can be managed with additional pain control interventions

- Persistent headache; infrequent, but it could be more serious and require follow up with anesthesiologist
- Infection; rare, and is serious, requiring additional care by physicians
- Temporary hip/leg discomfort; likely, but can be managed with additional pain control interventions and should go away on its own
- Low blood pressure; common, but can be treated with additional interventions
- Decrease in the baby's heart rate; infrequent, but it could be serious and require additional interventions

To minimize any risks, the research team will place epidural catheter according to standard clinical protocol including:

- Ask patients and monitor their pain control and clinical status, performing other interventions if needed
- Use aseptic technique

Additionally, there may be a loss to confidentiality and privacy. See *Minimizing the Risk for Subjects* for how the study team will minimize these risks.

As with any procedure, there may be additional risks that are unknown or unexpected but rare.

*Equitable Selection of Subjects*

All patients receiving epidural analgesia are candidates for this study. There are no patient factors that would be grounds for exclusion. No groups of persons based on gender, race, or any other distinction will be specifically targeted or excluded. Both epidural kits are current standard of care, thus there is no additional risk incurred due to participation in the study.

#### *Costs*

No additional cost will be incurred for the study.

#### *Data and Safety Monitoring Plan*

There are no plans for an independent data and safety monitoring board for this study. The principal investigator or the co-investigators will review analysis of all source data for each study subject when approximately half (n=120) of the epidural placements are completed. The principal investigator and the co-investigator will determine whether the research should be altered or stopped on an ongoing basis.

#### *Adverse Event Reporting*

The principal investigator will be responsible for reporting all adverse events according to the human research committee's guidelines.

#### *Monitoring and Quality Assurance*

The accuracy and completeness of all documents will be monitored on an on-going, weekly basis by the principal and co-investigator. All data will be collected at the time of each epidural placement, analyzed for completeness, and filed. The principal investigator and co-investigators will follow the validity and integrity of the data and adherence to the IRB approved protocol.

## TABLES

**Table 1 Inability to advance epidural catheters according to physician level of training**

Physician level	Single-orifice Incidence	Multi-orifice Incidence	Statistics
First-year resident	x/X (x%)	x/X (x%)	p=
Second-year resident	x/X (x%)	x/X (x%)	p=
Third-year resident	x/X (x%)	x/X (x%)	p=
Fellow	x/X (x%)	x/X (x%)	p=
Attending	x/X (x%)	x/X (x%)	p=

Data are number (%).

**Table 2 Demographic and Epidural data collection**

Characteristics	Single-orifice N=125)	Multi-orifice N=125)	P-value
Demographics			
Age, years	XX ± X	XX ± X	X
Body Mass Index, kg/m 	XX ± X	XX ± X	X
Gestational age, weeks	XX ± X	XX ± X	X
Pain relief within 30 minutes	X (x%)	X (x%)	X
Cervical dilation (cm)	XX ± X	XX ± X	X
Catheter failure to advance	X (x%)	X (x%)	X
Dural puncture epidural	X (x%)	X (x%)	X
Accidental dural puncture	X (x%)	X (x%)	X
Paresthesia	X (x%)	X (x%)	X
Intravascular cannulation	X (x%)	X (x%)	X
Time to catheter thread	X (x%)	X (x%)	X
Number of epidural attempts	X (x%)	X (x%)	X
Epidurals replaced	X (x%)	X (x%)	X

**Table 3 Success rates and complications of corrective maneuvers performed**

Maneuver	Single-orifice		Multi-orifice		Statistics
	Success (%)	Complications	Success (%)	Complications	
Saline injection	x/X (x%)	X	x/X (x%)	X	p=
Rotate needle bevel	x/X (x%)	X	x/X (x%)	X	p=
New placement	x/X (x%)	X	x/X (x%)	X	p=
Re-engage ligament, re-advance	x/X (x%)	X	x/X (x%)	X	p=
Advance needle	x/X (x%)	X	x/X (x%)	X	p=
Change needle angle	x/X (x%)	X	x/X (x%)	X	p=
New catheter	x/X (x%)	X	x/X (x%)	X	p=

Data are number (%).

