Once, the epidural catheter has been threaded successfully, the clinician will apply negative pressure to the catheter through a syringe in order to rule out blood or cerebro-spinal fluid (CSF) aspiration. If aspiration of blood and CSF is negative, the patient will be given our standard medications consisting of 2 ml Lidocaine 1.5% with epinephrine 1:200,000 to rule out intrathecal catheter placement. Following 2 minutes, the patients will be given additional 3 ml from the lidocaine and epinephrine mixture in order to rule out intravascular cannulation. In addition, a standard loading bolus of bupivacaine 0.125% with fentanyl 3 mcg/ml will be administered in three fractionated doses of 5 ml each, through an epidural pump. All patients will be then connected to a programmed intermittent epidural bolus pump with the following settings: bupivacaine 0.125% with fentanyl 3 mcg/ml, programmed intermittent bolus 6 ml every 45 minutes. Patient's demand bolus 6 ml every 15 minutes, without baseline infusion.

If the epidural catheter cannot be sufficiently advanced into the epidural space, one or more of the following maneuvers will be adopted: additional saline will be administered through the Tuohy needle; alternatively, a new flexible epidural catheter can be inserted; if the catheter advances following one of these afore-mentioned maneuvers, the thread will be considered successful with minor adjustments. Conversely, if the needle is rotated, re-angled, redrawn and

re-advanced or advanced blindly, these will all be considered as major needle manipulations and recorded as failure of that attempt to advance the epidural catheter. Further attempts are made until proper epidural analgesia is established.

Establishment of successful labor analgesia will be defined at a verbal analogue score equal to or less than 10 on a 100-point scale within 30 min from the standard epidural medication administration. All data related to the technical aspects of the epidural placement will be collected in the form shown in the appendix. The goal of both study groups is the management of labor pain.

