### *Study Size*

In order to determine the study size, we looked at 114 consecutive epidural placements as part of our routine quality assurance with the Arrow® Epidural Catheterization Kit at Von Voigtlander. We found that in 11% (n=12) of epidurals placed, the epidural catheter did not thread on the first attempt. In a separate quality assurance check we retrospectively reviewed 100 epidural placements finding out that in 1% (n=1) of epidurals placed, the epidural catheter did not thread on the first attempt. A sample-size analysis for the primary outcome shows that 107 epidural placements per group would provide a power of 80% to detect a difference in proportion between the two techniques of 0.10 at the 0.05 level. Considering an attrition of 10-20% for follow-up and data missing, a total number of 240 epidural placements will be collected. Power calculations were computed using PASS 14.

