### *Statistical Analysis*

Statistical analysis will be performed using SAS 9.3 (SAS Institute, Cary, NC). The

primary outcome will be the success rate of epidural catheter threaded with each epidural kit, which will be compared by group using a chi-square test or Fisher's exact test, as appropriate. The secondary outcomes will be analyzed as follows: the difference in number of epidural attempts will be compared using the Mann-Whitney test; the difference in time to perform the epidural start to finish defined as the time the epidural needle is inserted through the patient's skin to the end of the catheter thread will be compared using the Student's t-test; the difference in the incidence of epidural needle manipulations once the epidural space has been established will be compared using the Chi-Square or Fisher's exact test, as appropriate; the difference in incidence of unintended dural puncture, paresthesia, and intravascular cannulations will be compared using the chi-square or Fisher's exact test, as appropriate. In addition, the difference in unsatisfactory labor analgesia with Arrow® and B.Braun® kits will be compared through the chi-square or Fisher's exact test, as appropriate, by looking at the difference in percentages of patients who have a verbal analogue pain score equal or less than 10 (scale 0 to 100) at 30 minutes following epidural medication administration. A p-value of 0.05 throughout will be considered statistically significant.

All statistical analyses will be performed using SAS 9.3 (SAS Institute, Cary, NC).

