## Ease of Threading the Epidural Catheter

- |   |                              |
|---|------------------------------|
|  Easy thread without further maneuvers  |                              |
|  hydrodissection, then catheter:  | Thread Did not thread |
|  new catheter from the same brand, then catheter:   | Thread Did not thread |
|  Rotated the needle, then catheter:   | Thread Did not thread |
|  Changed needle angle, then catheter:   | Thread Did not thread |
|  Withdrawal and re-advanced the needle with an additional LOR (this count as an additional attempt), then catheter: | Thread Did not thread |
|  Advanced the needle blindly, then catheter:  | Thread Did not thread |
|  Changed space  |                              |

Patient Comfort at 30 minutes (VAS  $\leq$  10/100) YES NO

Additional Number of attempts after loss of resistance 0 1 2 3 4 5

Complications (circle all that applies)

Wet tap Paresthesias Intravascular Other (please explain)

Epidural analgesia failed and then epidural Replaced? YES NO

Delivery date \_\_\_ and Time \_\_\_\_\_

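### Table 3 plans complication counts for each corrective maneuver by kit, but the study form records complications once per placement with no link to a maneuver

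*Combined protocol and SAP*

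**What the plan says.** Table 3 is headed "Success rates and complications of corrective maneuvers performed". Its seven rows are saline injection, rotating the bevel, new placement, re-engaging the ligament and re-advancing, advancing the needle, changing the angle, and a new catheter. Each row has a success cell and a complications cell per kit, and one statistics cell.

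The section Equipment, Technique and Study Data Collection names the source: "All data related to the technical aspects of the epidural placement will be collected in the form shown in the appendix". It also says that when the catheter does not advance, "one or more of the following maneuvers will be adopted", so one placement can contribute to several rows.

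On the form, under Ease of Threading the Epidural Catheter, each maneuver has a tick box (for example "hydrodissection, then catheter"). Six of the seven boxes carry a result, threaded or not. The seventh, Changed space, carries none. Complications appear once, further down, as "Complications (circle all that applies"), with the options "Wet tap Paresthesias Intravascular Other (please explain").

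The Statistical Analysis section plans complication comparisons between kits only: "the difference in incidence of unintended dural puncture, paresthesia, and intravascular cannulations will be compared using the chi-square or Fisher's exact test". It gives no rule for assigning a complication to a maneuver.

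**The concern.** A reader will take Table 3 as a statement about how safe each maneuver was with each kit. That needs to be known event by event: did the complication follow this maneuver, another one, or the needle advance before any maneuver? The form does not ask. A wet tap on the original needle advance is recorded in the same way as one during a later maneuver.

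An analyst filling the table must therefore either enter one event under every ticked maneuver or guess. The first inflates the counts. The second is not reproducible. The timing is known to the operator at the bedside and cannot be reliably recovered afterwards.

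**Working it through.** The plan gives no figure for this point, so the check is mainly a mapping of Table 3 onto the form.

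**1. Complications cells.** Needed: maneuver, kit and event. Collected: kit, the set of maneuvers ticked, and the set of complications circled for the placement. The request to explain attaches only to the Other option, so a wet tap, paresthesia or intravascular event prompts no narrative. The field for additional attempts after loss of resistance gives a number, not a timing.

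**2. What one wet tap or paresthesia looks like in the data.** Suppose k maneuvers are ticked and one such event is circled.

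- Timings that fit the form: before any maneuver, or with any one of the k, so k + 1.
- Entries in a simple cross-tabulation: k.

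| k | compatible timings | entries from one event |
|---|---|---|
| 1 | 2 | 1 |
| 2 | 3 | 2 |
| 3 | 4 | 3 |

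Even with k = 1 the attribution is not settled.

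**3. How much order can be recovered.** For the six maneuvers with a result, the one marked as threaded came last, unless a threaded catheter was later replaced. The other k − 1 can then fall in (k − 1)! orders: 1 for k = 2, 2 for k = 3, 6 for k = 4. Order is thus fixed for two maneuvers and only partly known from three upward. Knowing the order still does not date a wet tap or paresthesia.

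**4. Success in the New placement row.** The Background section describes a new placement as being at the same or a different interspace. The form's nearest item, Changed space, has no result field, and a new placement at the same space has no box of its own. If Changed space is ticked and every other ticked maneuver is marked as not threading, success can be inferred, because attempts continue until analgesia is established. If further maneuvers were used at the new space, it cannot.

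**5. Illustrative size.** Study Size reports for Arrow: "We found that in 11% (n=12) of epidurals placed, the epidural catheter did not thread on the first attempt", from 114 placements (12/114 = 10.5%, given as 11%). A second check gives 1 of 100 (1%). With 120 placements per kit:

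- 120 × 0.11 = 13.2
- 120 × 0.01 = 1.2

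The documents give no complication rate. If 5% to 20% of the 13.2 placements had a complication (an assumption), that is 13.2 × 0.05 = 0.66 to 13.2 × 0.20 = 2.64 events. With counts this small, one event entered three times or left out changes a cell materially.

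**The case against.** The strongest reply is that no stated endpoint depends on these cells. The Objectives and Statistical Analysis sections compare dural puncture, paresthesia and intravascular cannulation by kit, and Table 2 reports them by kit. One list per placement is enough for that. This stands. A reader might infer from the mismatch that the planned safety comparisons are compromised; the documents do not support that.

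Second, the form is not silent on timing. The protocol places aspiration and the intravascular test dose after the catheter has threaded, so an intravascular event would normally belong to the pass that threaded, unless an earlier catheter was replaced. This also stands, and it narrows the attribution problem to wet tap and paresthesia.

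Third, the column header is undefined. It could mean placements in which the maneuver was used and a complication was circled, and the form can supply that. But Table 3 is not labelled so, the count repeats events, and it includes events from before the maneuver. A footnote would prevent misreading without supplying the timing.

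Two further inferences are tempting and unsupported. One is that the table would be biased against maneuvers used late, or against one kit. Counting by co-occurrence charges every ticked maneuver, early or late, so that direction is not shown. The other is that the New placement success cells cannot be filled at all; some can, by inference.

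**Conclusion.** The point holds, within Table 3. Followed as written, the plan gives per-maneuver complication counts that are either multiply counted or guessed, and a New placement success row that rests partly on inference. The primary outcome and the by-kit complication comparisons do not change.

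The mapping rests only on the printed table and form. The counts of about 13 and 1 placements per 120 are illustrative. They assume that the quality-assurance rates carry over to the two arms, and Study Size does not name the kit behind the 1%. It also does not say whether the 11% includes placements rescued by saline or a new catheter, which the protocol classes as successful with minor adjustments but which do enter Table 3. The number reaching the table could therefore differ from 13.

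**What to change.** On the form:

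- Number the maneuvers in the order used.
- Beside each maneuver, add a complication code (wet tap, paresthesia, intravascular, other), and add one line for events before or at the first threading attempt.
- Add a threaded / did not thread result for a new placement, with separate boxes for the same and a different space.

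If the form is not changed, drop the complications columns from Table 3 and report complications per placement by kit, split by any versus no maneuver. The form already supports that split, since it has a box for an easy thread with no maneuver. The split remains descriptive, because an event in the any-maneuver group may have preceded the maneuver.

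The cost is a one-page form revision, best made before the first placement, and a few more seconds of completion in placements where a maneuver is used. Sample size, randomization and the planned tests stay as they are.

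### Table 3 tests kit differences in manoeuvre success only among placements whose catheter did not advance at first, so its seven p-values are not randomised comparisons and, at the likely counts, carry almost no information

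*Combined protocol and SAP*

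**What the plan says.** Table 3, "Success rates and complications of corrective maneuvers performed", has seven manoeuvre rows. For each kit (labelled single-orifice and multi-orifice) it shows success as x/X and a complications count, and each row ends in a Statistics cell holding a p-value.

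Equipment, Technique and Study Data Collection defines who enters the table: "If the epidural catheter cannot be sufficiently advanced into the epidural space, one or more of the following maneuvers will be adopted". The data form agrees, since it lists an easy thread without manoeuvres separately from the manoeuvre lines.

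Statistical Analysis names no analysis set or test for manoeuvre success. It sets one threshold for everything: "A p-value of 0.05 throughout will be considered statistically significant". Nothing labels Table 3 descriptive.

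Study Size gives the two planning rates. The first is from 114 Arrow placements: "We found that in 11% (n=12) of epidurals placed, the epidural catheter did not thread on the first attempt". The second is from a separate review of 100 placements whose kit is not named: "in 1% (n=1) of epidurals placed, the epidural catheter did not thread on the first attempt".

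On the form, six manoeuvre lines offer a choice of thread or did not thread. The line "Changed space" has no such choice.

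**The concern.** The kits are randomised by week over all placements, but Table 3 compares them only where the catheter did not advance initially. The kit helps decide which placements those are. If one kit fails less often, its failures may differ in kind from the other kit's, so a difference in manoeuvre success could reflect which cases were left rather than how well the manoeuvre works with that kit. Weekly randomisation does not protect such a comparison.

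The second problem is information. The planning rates suggest very few placements in one column, spread over seven rows. With a 0.05 threshold applied throughout, a reader could take seven non-significant rows as evidence that rescue works equally well with both kits, or a stray significant row as a kit effect. Neither would be justified.

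**Working it through.** **Inputs.** First-attempt failure 11% for Arrow (12/114 = 10.5%) and 1% (1/100) for an unnamed kit, both from Study Size; 120 placements per kit, from Randomization Procedure; threshold 0.05, from Statistical Analysis. Assumption: the 1% rate belongs to B.Braun.

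**Reproducing the plan's own figure.** Study Size states that "107 epidural placements per group would provide a power of 80% to detect a difference in proportion between the two techniques of 0.10". Take p1 = 0.11, p2 = 0.01, mean 0.06, two-sided 0.05.

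- Uncorrected: n = [1.96 × √(2 × 0.06 × 0.94) + 0.842 × √(0.11 × 0.89 + 0.01 × 0.99)]² / 0.10² = 87.3, so 88.
- Continuity-corrected: (87.3/4) × [1 + √(1 + 4/(87.3 × 0.10))]² = 106.4, so 107.

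The stated 107 is reproduced by 11% v 1%, so these are evidently the rates planned on.

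**Placements entering Table 3.** 120 × 0.11 = 13.2 and 120 × 0.01 = 1.2, about 13 v 1 for the whole table. Any single row can only have the same number or fewer.

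**Smallest attainable Fisher p-value.** With unequal denominators a and b, the most extreme table (all succeed with one kit, none with the other) has two-sided p = 1/C(a+b, b) in the cases below. With equal denominators it is twice that.

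| Denominators | Smallest p |
|---|---|
| 13 v 1 | 1/14 = 0.071 |
| 6 v 1 | 1/7 = 0.143 |
| 20 v 1 | 1/21 = 0.048 |
| 13 v 2 | 1/105 = 0.0095 |
| 5 v 2 | 1/21 = 0.048 |
| 4 v 4 | 2/70 = 0.029 |
| 2 v 2 | 2/6 = 0.33 |

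An uncorrected chi-square on 13/13 v 0/1 gives p = 0.0002, but it is invalid with such small expected counts. With Yates' correction p = 0.084.

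**Chance variation in the counts.** For Binomial(120, 0.01):

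- P(0) = 0.99^120 = 0.30
- P(1) = 120 × 0.01 × 0.99^119 = 0.36
- P(2 or more) = 1 − 0.30 − 0.36 = 0.34

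With exactly one failure in that arm, 0.05 needs at least 20 Arrow failures, which has probability 0.039. Summing over both binomials gives the chance that p < 0.05 is attainable at all in a row. The last column is Fisher power if true manoeuvre success were 90% v 10%. The usage shares and success rates are assumptions.

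| Share of failures receiving the manoeuvre | P(0.05 attainable) | Power, 90% v 10% |
|---|---|---|
| All | 0.35 | 0.21 |
| Half | 0.10 | 0.05 |
| One-seventh | 0.0006 | 0.0003 |

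**If both kits failed at 11%.** About 13 v 13 placements would enter. A row with 4 v 4 could reach 0.029; a manoeuvre used in one-seventh of failures (about 2 v 2) could not go below 0.33.

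**Possible direction of bias (illustration only).** Suppose difficulty is standard normal and shared by both kits, failure occurs above the 89th or the 99th percentile, and manoeuvre success is logistic in (intercept − slope × difficulty), identical for both kits. Apparent success with the 11% kit v the 1% kit is then:

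| Intercept | Slope | Apparent success |
|---|---|---|
| 2.25 | 0.5 | 80% v 71% |
| 2.5 | 1.0 | 68% v 46% |
| 2.75 | 1.5 | 55% v 23% |
| 5 | 1.0 | 96% v 91% |

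Under this model the kit that fails less often looks worse at rescue, by an amount that depends heavily on inputs the documents do not supply.

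**The case against.** Four objections deserve weight.

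First, a reader might infer that no row can ever reach 0.05. The documents do not support that. It is true at 13 v 1, but two or more failures in the 1% arm have probability 0.34, and the 1% rate is not tied to a kit. The protocol's stated hypothesis is no difference, and with similar failure rates a well-used row could be significant.

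Second, a reader might infer that Table 3 is selected exactly on the primary outcome. That holds under the first-attempt definition in Background and Study Size. The technique section instead counts a thread after saline or a new catheter as successful with minor adjustments, so on that reading the saline and new-catheter rows can include primary-outcome successes. These placements are still a post-allocation subset that did not advance at first, so the selection problem stands.

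Third, a reader might infer that the better kit will look worse at rescue. That needs one difficulty scale shared by both kits. Their needles and catheter tips differ, so their failures could have different causes. The direction is an assumption; the absence of randomised protection is not.

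Fourth, manoeuvre success is not a listed objective, and the plan already compares needle manipulations by kit and shows failure to advance by arm in Table 2. This limits the consequence. It does not explain why Table 3 carries p-values.

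On the form, it would also go too far to say that the New placement row cannot be filled. Background allows a new placement at the same or another interspace, and the form records additional attempts and replacement, so some outcomes may be recoverable.

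**Conclusion.** The concern holds in a limited form. The seven p-values in Table 3 compare kits within a subset that forms after allocation and that the kit can alter. They are not randomised comparisons and may be biased in a direction the documents cannot settle. This rests only on the rule for when a manoeuvre is used and on the table shell, not on any failure rate.

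That the tests are also nearly uninformative depends on assigning the 1% rate to B.Braun. On that assumption the expected counts are about 13 v 1 with a smallest Fisher p-value of 0.071, and the chance that a row could reach 0.05 runs from 0.35 down to 0.0006 as the manoeuvre's use falls from all failures to one-seventh of them. If both kits failed near 11%, this part weakens and the first part remains.

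The primary analysis is not affected. The change is worth making because the table as specified invites a misleading reading and correcting it is nearly free.

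**What to change.** 1. Delete the Statistics column from Table 3. Present the table as descriptive counts, and state each denominator: placements with that kit in which the catheter did not advance and that manoeuvre was used.
2. For the kit comparison, report the share of all placements in each arm that needed any corrective manoeuvre, and the share that needed each type, with the between-kit difference and its interval. This extends the needle-manipulation comparison already in Statistical Analysis and keeps the full arm as denominator.
3. State whether a thread after saline or a new catheter counts as a success for the primary outcome, so that the make-up of those two rows is clear.
4. Add the thread / did not thread choice to the form's "Changed space" line, so that the success of a new placement at another interspace is recorded directly.

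The cost is an edit to one table shell, a sentence or two in Statistical Analysis and one tick-box. No further placements are needed. The downside is the loss of seven p-values.
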